## 9.5 STUDY SIZE

It is planned to collect 300 patients.

A sample size of 300 patients was planned in consideration of post-marketing occurrence of haemorrhagic events observed for Prazaxa® (based on the periodic safety update reports) and on the basis of feasibility.

Important potential risks (thrombosis and hypersensitivity) are considered as the key survey items. If real incidence rates of thrombosis and hypersensitivity in Japanese patients are same

as shown in the interim data in Study 1321.3 (5.3% and 12.3%) [[c03666927-01](#)], 95% confidence interval of their incidence rate is shown in the [Table 2](#).

To ensure the same accuracy of the estimation (95% confidence interval: 2.8% to 9.0% (thrombosis), 8.4% -17.1% (hypersensitivity) in this study, about 250-300 cases is required with conservative estimation. Further, with a sample size of 300 patients, any ADR with frequency of 1% or higher can be detected with probability of 95% or greater in at least one patient.

Table 2 95% confidence interval of the incidence rate

N	Incidence rate	95% confidence interval		Upper-Lower
		Lower	Upper	
Thrombosis				
100	5.30%	1.7%	11.8%	10.1%
150	5.30%	2.2%	10.3%	8.1%
200	5.30%	2.6%	9.4%	6.8%
250	5.30%	2.9%	8.9%	6.0%
300	5.30%	3.0%	8.5%	5.5%
350	5.30%	3.2%	8.2%	5.0%
400	5.30%	3.3%	8.0%	4.7%
Hypersensitivity				
100	12.30%	6.5%	20.5%	13.9%
150	12.30%	7.5%	18.7%	11.2%
200	12.30%	8.1%	17.7%	9.6%
250	12.30%	8.5%	17.0%	8.6%
300	12.30%	8.8%	16.6%	7.8%
350	12.30%	9.0%	16.2%	7.2%
400	12.30%	9.2%	15.9%	6.7%

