## 9.7 DATA ANALYSIS

This is a non-interventional study based on new data collection to gather data on safety and effectiveness of the Prizbind® for Intravenous Solution 2.5 under Japanese clinical condition. Analyses for safety, effectiveness and baseline characteristics are descriptive in nature including means, standard deviation, min, Q1, medians, Q3, max, frequency and percentages.

Per local regulation, any patient who meets at least one of the following criteria is treated as ineligible for all analyses:

- No follow-up visit data are available
- No required registration procedure is followed
- No valid site contract is available

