### 9.7.1 Main analysis

All outcome events are based on reported AE data which will be handled according to BI standards (see the section below).

[figure not shown]
The safety analysis will include all patients who registered, received the Prizbind® for Intravenous Solution 2.5 g treatment and collected CRF except for who meet the ineligible criteria (see Section 9.7).

[figure not shown]
AEs will be coded using the current version of the Medical Dictionary for Regulatory Activities (MedDRA). Based on the concept of treatment emergent AEs, all AEs occurring between first intake of Prizbind® for Intravenous Solution 2.5 g prescribed at baseline visit up to 5 days after the last intake will be considered 'treatment period'. In addition, AEs with onset date before start of the trial treatment but with worsening in intensity during the treatment will also be assigned to the on-treatment period. Other AEs will be assigned to the screening or post-treatment period, respectively.

An AE is considered to be an ADR if either the physician who has reported the AE or the sponsor assesses its causal relationship as 'related'.

The frequency and percentages of ADRs, SAEs, and other AEs occurred in treatment period as well as treatment + post-treatment period will be tabulated by system organ class and preferred term for all patients and for subgroups based on the important baseline characteristics (details will be described in the TSAP).

No imputation is planned for missing AE data except for missing onset dates which will be handled according to BI standard.

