7. PLANNED ANALYSIS

For End-Of-Text (EoT) tables, the set of summary statistics is: N / Mean / SD / Min / Q1 / Median / Q3 / Max.

For tables that are provided for endpoints with some extreme data, median, quartiles and percentiles should be preferred to mean, standard deviation, minimum and maximum.

Tabulations of frequencies for categorical data will include all possible categories and will display the number of observations in a category as well as the percentage (%) relative to the respective treatment group (unless otherwise specified, all patients in the respective patient set whether they have non-missing values or not). Percentages will be rounded to two decimal places. The category missing will be displayed only if there are actually missing values.

Tables will be displayed by purpose of use (Group A, Group B, Group A+B, Other and All) categorized by trial team.

In addition, individual values on demographics, safety and effectiveness will be presented in subject data listings.

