7.8.1 Adverse events

Unless otherwise specified, the analyses of adverse events (AEs) will be descriptive in nature. All analyses of AEs will be based on the number of patients with AEs. In the tabulation of ADRs, serious ADRs, important identified risks and important potential risks by SOC and PT, not only the number of patients but also number of events will be displayed. AEs with onset date prior to treatment of Prizbind which lead to death after Prizbind administration are not included in AE analysis but will be used when calculating time to death using Kaplan Meier survival estimates.

For analysis multiple AE occurrence data on the CRF will be collapsed into an AE provided that all of the following applies:

- All AE attributes are identical (LLT, intensity, action taken, therapy required, seriousness, reason for seriousness, relationship, outcome).
- The occurrences were time-overlapping or time-adjacent (time-adjacency of 2 occurrences is given if the second occurrence started on the same day or on the day after the end of the first occurrence).

For further details on summarization of AE data, please refer to (2).

All adverse events occurring after the residual effect period will be assigned to 'post-treatment. The frequency and percentages of ADRs, AEs, serious adverse events (SAEs), important identified risks and important potential risks occurred in treatment + post-treatment period as well as treatment period will be tabulated. For details on the treatment definition, see [Section 6.1](#). Also, ADRs and SAEs up to 28 days after last treatment intake (=observation period) will be tabulated.

An overall summary of AEs will be presented.

The frequency of patients with ADRs will be tabulated by Prizbind dose at onset, SOC and PT according to the most recent MedDRA version.

Separate tables will be provided for patients with SAEs, serious ADRs and for patients with each of the following AEs for important identified risks: hypersensitivity (shock and anaphylaxis) and important potential risks: immunogenicity, thrombotic event (ischemic stroke, myocardial infarction, pulmonary embolism, deep vein thrombosis, systemic embolism). Important identified risks and important potential risks are defined in accordance with the Japanese RMP. The details of these risks are defined in the external file

‘MedDRA_verxxx.xlsx (current ver.)’. The file is stored in BIRDS ‘Section 8 TSAP and programming’.

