For AEs leading to discontinuation of Prizbind, a summary table will also be created based on patients who discontinued the treatment due to AEs.

In addition, summaries for the time to onset of first episode for the ADRs will be tabulated by duration, by primary SOC, and PT.

An ADR is defined as an AE for which either the investigator or the sponsor (or both) assess the causal relationship to Prizbind as “Yes”. The SOCs will be sorted according to the standard sort order specified by European medicines agency, PTs will be sorted by frequency (within SOC).

A serious AE is defined as an AE for which either the investigator or the sponsor (or both) assess the seriousness as “Serious”.

Mortality rate at the end of follow-up period will be calculated descriptively by KM estimate. It will be also stratified by ICH, upper or lower GI bleeds on-going at baseline assessment and other for Group A and Group A+B categorized by trial team.

To compare risks of overall ADR, SAE, serious ADR as well as each of the important potential risks in different patient subgroups, frequency tabulation stratified by different patient subgroups will be provided with odds ratios and exact 95% confidence intervals whenever specified (see [Section 6.4](#)).

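### Read literally, the SAP's subgroup odds-ratio sentence omits hypersensitivity, one of the two key survey items; secondarily, the visible analysis text names no confidence interval for either item's overall incidence

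*SAP*

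**What the plan says.** **How the risks are classed.** Protocol 9.5 states: "Important potential risks (thrombosis and hypersensitivity) are considered as the key survey items". Protocol 9.3.2.1 also lists hypersensitivity among the important potential risks, and adds that immunogenicity will be judged from the clinical manifestations of hypersensitivity. SAP 7.8.1, following the Japanese RMP, instead separates "important identified risks: hypersensitivity (shock and anaphylaxis) and important potential risks: immunogenicity, thrombotic event".

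**What is tabulated.** SAP 7.8.1 plans "The frequency and percentages of ADRs, AEs, serious adverse events (SAEs), important identified risks and important potential risks occurred in treatment + post-treatment period" and, equally, in the treatment period. Both risk classes are named there.

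**What is compared between subgroups.** The later sentence in SAP 7.8.1 begins "To compare risks of overall ADR, SAE, serious ADR as well as each of the important potential risks in different patient subgroups". It offers odds ratios with exact 95% confidence intervals where specified, and refers to Section 6.4. Identified risks are not named.

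**Sizing and reporting.** Protocol 9.5 argues for about 250 to 300 cases with the words "To ensure the same accuracy of the estimation (95% confidence interval: 2.8% to 9.0% (thrombosis), 8.4% -17.1% (hypersensitivity) in this study". It also cites haemorrhagic-event occurrence, feasibility and detection of a 1% ADR. Protocol 9.7 says "Analyses for safety, effectiveness and baseline characteristics are descriptive in nature including means, standard deviation, min, Q1, medians, Q3, max, frequency and percentages".

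**The concern.** The SAP moved hypersensitivity from one risk class to the other, and one sentence does not reflect the move. A programmer who follows that sentence would produce odds ratios for thrombotic event and immunogenicity but none for hypersensitivity as its own category. The two items that the protocol puts on an equal footing would then be reported unequally.

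The secondary matter is a mismatch between sizing and reporting. Every row of Protocol Table 2 is a confidence interval for the incidence of one of these two risks. The analysis text in Protocol 9.7 and 9.7.1 and SAP 7 and 7.8.1 names summary statistics, counts and percentages. The only intervals it names belong to subgroup odds ratios, and those do not describe the precision of an overall incidence.

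**Working it through.** **Step 1. Set the sentences side by side.**

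| Place | Hypersensitivity classed as | Classes the sentence covers |
|---|---|---|
| Protocol 9.3.2.1, 9.5 | potential | potential |
| SAP 7.8.1, tabulations | identified | identified and potential |
| SAP 7.8.1, subgroup odds ratios | identified (same section) | potential only |

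Under the SAP's own classes, the third row covers immunogenicity and thrombotic event. Hypersensitivity is the one named risk of three that falls outside it.

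**Step 2. Check what still reaches hypersensitivity.**
- Events that are ADRs or SAEs count in the overall ADR, SAE and serious ADR comparisons.
- Some events may enter through immunogenicity, given how Protocol 9.3.2.1 assesses it.
- Protocol 9.7.1 tabulates AEs "for all patients and for subgroups based on the important baseline characteristics".
- SAP 7 says: "Tables will be displayed by purpose of use (Group A, Group B, Group A+B, Other and All) categorized by trial team".

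What is at risk is therefore only the separate odds-ratio comparison for hypersensitivity.

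**Step 3. Reproduce the plan's own intervals.** Inputs from Protocol 9.5: rates 5.3% and 12.3%, n = 300. The protocol does not name its method. The exact (Clopper-Pearson) limits are

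lower = Beta(0.025; x, n − x + 1), upper = Beta(0.975; x + 1, n − x), with x = n·p.

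- Thrombosis: x = 300 × 0.053 = 15.9, giving 3.05% to 8.48% (Table 2: 3.0% to 8.5%).
- Hypersensitivity: x = 300 × 0.123 = 36.9, giving 8.81% to 16.56% (Table 2: 8.8% to 16.6%).

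All 28 limits in Table 2 agree within 0.12 points, and within 0.06 points for n of 200 or more. Wilson limits at n = 300 (3.28% to 8.45%; 9.05% to 16.50%) and Wald limits (2.76% to 7.84%; 8.58% to 16.02%) fit less well. The thrombosis width at n = 300 computes to 5.42 points against 5.5 printed, so the match is on the limits and not on that width. The 1% detection claim also holds: 1 − 0.99^300 = 0.951.

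**Step 4. The intervals the report could carry**, using whole counts at the planning rates:
- 16/300 = 5.33%, exact 95% CI 3.08% to 8.52%, width 5.44 points.
- 37/300 = 12.33%, exact 95% CI 8.83% to 16.60%, width 7.76 points.

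The precision stated in 9.5 corresponds to widths of 9.0 − 2.8 = 6.2 points and 17.1 − 8.4 = 8.7 points. At the planning rates these are met from n = 234 (thrombosis) and n = 241 (hypersensitivity), so 300 leaves room for exclusions.

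**Step 5. What an interval would and would not show.** Width depends on the observed rate. With 3 events in 300 the exact interval is 0.21% to 2.89%, a width of 2.68 points. That is below both 6.2 and 8.7 only because the rate is low. A narrow interval describes the precision of the estimate obtained; it does not by itself show that the sizing assumption held.

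**The case against.** The strongest reply to the main point is that the odds-ratio sentence applies only where specified and refers to Section 6.4, which is not in the visible text. That section may list hypersensitivity. In the protocol's terms, moreover, the important potential risks include hypersensitivity, so the sentence may be meant in that sense. The SAP history table records that the risk definitions were added to 7.8.1 in the 2021 revision, which fits wording left over from before the addition, though that is an inference. This reply stands as a limit: the documents do not show what will actually be run. It does not remove the mismatch, because the SAP defines the classes in the same section that then uses them unevenly.

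On the intervals, sizing a descriptive survey by expected width does not oblige the plan to print them, and no visible sentence promises them. Protocol 9.7 introduces its list with a word that leaves it open, and SAP 7.8.1 sends further AE detail to a reference whose entry is not visible. A reader can also compute the intervals from the counts. All of this stands, which is why the interval is offered as an improvement and not as a defect.

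A reader might infer that the sponsor decided to drop hypersensitivity from subgroup analysis, or that the survey cannot deliver the precision it was sized for. The documents support neither. Hypersensitivity keeps its own table and subgroup breakdowns, and n = 300 meets the stated widths at the planning rates.

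**Conclusion.** The point holds as a minor wording mismatch. Taken literally, SAP 7.8.1 omits hypersensitivity as its own category from the subgroup odds ratios, while the other key survey item is included. No data are lost, no estimate is biased and the sample size is unaffected. The conclusion rests on the visible text alone; Section 6.4 could narrow or remove it.

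The missing overall intervals are secondary. They would add a direct statement of precision for the two incidences behind the sizing argument, but they should not be presented as proof that the target was reached. Two further unknowns limit their reading:
- The interim report and the MedDRA term file are not provided, so it cannot be judged whether the SAP's category of shock and anaphylaxis matches what the 12.3% planning rate counted.
- Protocol 11.2 requires CRF collection of ADRs and fatal AEs. Protocol 9.3.2.1 counts serious AEs and risk AEs as outcomes, and Protocol 9.4 and Table 1 call for adverse events generally. The basis on which non-fatal, unrelated events are ascertained is therefore unclear.

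**What to change.** 1. In SAP 7.8.1, extend the subgroup odds-ratio sentence to cover each important identified risk as well as each important potential risk, and align Section 6.4 if needed. Cost: one phrase.
2. Optionally, report an exact (Clopper-Pearson) 95% confidence interval with the overall incidence of thrombotic events and of hypersensitivity, labelled as the precision of the estimate. Cost: two intervals on incidences already tabulated.
3. Reconcile Protocol 11.2 with Protocol 9.3.2.1, 9.4 and Table 1 on which adverse events the CRF collects. Then state the resulting ascertainment basis in a note under the two incidences. Cost: one clarification and one note.

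None of these needs new data or a change to the sample size.

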7.8.2 Laboratory data

Only clinically relevant findings reported as AE will be analysed as a part of AE analyses.

7.8.3 Vital signs

Only clinically relevant findings reported as AE will be analysed as a part of AE analyses.

[figure not shown]
7.8.4 ECG

Only clinically relevant findings reported as AE will be analysed as a part of AE analyses.

7.8.5 Others

No other analysis is planned.

8. REFERENCES

10. HISTORY TABLE

This is a revised TSAP including the following modifications to the final TSAP.

Table 10: 1 History table

Version	Date (DD-MMM-YY)	Author	Sections changed	Brief description of change
Final	17-Apr-2019	[REDACTED]	None	This is the final TSAP without any modification
Revised	19-Mar-2021	[REDACTED]	2 6.3 6.6 7.2 7.8.1 8	Abbreviations not used in TSAP are removed. [REDACTED] Table 6.3: 1 is rearranged due to addition of new group. [REDACTED] Modification in Section 5.4 is reflected. Imputation rules for time to re-start anticoagulant therapy are deleted. Description for definition of concomitant diseases is added. [REDACTED] Description for number of events is added. Analyses for important identified risks and important potential risks occurred in treatment + post-treatment period are added. Description for definition of important identified risks and important potential risks is added. Reference sources are modified.
